ABBREVIATIONS LIST

Abbreviation	Definition
°C	degrees Celsius
µM	Micromolar
20S	20S proteasome subunit
AE	adverse event
ANC	absolute neutrophil count
Bc1-2	B-cell lymphoma-2; a gene that inhibits apoptosis
BSA	body surface area
Bu	busulfan
CAM	cell adhesion molecules
cm	Centimeter
CR	Complete Response
CTCAE	(NCI) Common Terminology Criteria for Adverse Events
CTEP	Cancer Therapy Evaluation Program
dL	Deciliter
DLT	Dose Limiting Toxicity
DNA	deoxyribonucleic acid
FDA	Food and Drug Administration
Flu	fludarabine
GCP	Good Clinical Practice
GLP	Good Laboratory Practice
ht	Height
IκB	I kappa B kinase; cytokine response kinase that activates transcription factor NF-kappa b at serine 32 and 36
ICAM-1	intercellular adhesion molecule 1
ICH	International Conference on Harmonisation
IEC	Independent Ethics Committee
IND	Investigational New Drug
IRB	Institutional Review Board
IV	Intravenous
IκBα	I kappa B alpha-associated protein kinase
kg	Kilogram
Ki	inhibitory constant
lbs	Pounds

Abbreviation	Definition
m ²	square meters
mg	Milligram
min	Minute
mL	Milliliter
mm ³	cubic millimeters
mmol	Millimole
MTD	Maximum Tolerated Dose
NCI	National Cancer Institute
NF-κB	nuclear factor-κB
ng	Nanogram
nM	Nanomole
p21	p21(ras) farnesyl-protein transferase
p27	cyclin-dependent kinase inhibitor
p53	tumor suppressor protein with molecular weight of 53 kDa
SAE	serious adverse event
TBI	total body irradiation
US	United States
USP	United States Pharmacopeia
VCAM-1	vascular cell adhesion molecule 1
w/w	weight-to-weight ratio
wt	Weight

1 INTRODUCTION AND STUDY RATIONALE

1.1 Allogeneic transplantation for the treatment of myelodysplastic syndrome, chronic myelogenous leukemia and other myeloproliferative disorders, and acute myeloid leukemia:

The myelodysplastic syndromes are a heterogeneous group of clonal hematologic disorders characterized by bone marrow failure and proliferation of myeloblastic leukemia cells. Patients with MDS develop cytopenias as a result of ineffective hematopoiesis. These cytopenias are believed to be a result of an increase in apoptosis resulting in an increase in futile cell cycling. In addition, the apparently mature and differentiated hematopoietic cells in patients with MDS are functionally impaired. Granulocytes have decreased myeloperoxidase activity (1,2) and platelets have impaired function. Therapy for MDS includes supportive care geared mostly to transfusional support. Allogeneic transplantation has been shown to offer the possibility of long-term remission and remains the only curative option for patients with MDS. The development of reduced intensity conditioning

regimens expanded the scope of allogeneic transplantation for older patients with MDS. A very large retrospective analysis by the European Blood and Marrow Transplantation Group (3) compared the outcome of 836 patients with MDS treated with either a reduced-intensity conditioning regimen or a conventional regimen before allogeneic transplantation. The 3-year probabilities of progression-free and overall survival were similar in both groups, with a 3-year relapse rate being significantly higher in the reduced-conditioning group, offset by a significantly reduced probability of non-relapse mortality. This demonstrates the importance of the preparative regimen in preventing relapse in this setting.

Acute myeloid leukemia accounts for over 9,000 deaths yearly in the United States. The WHO classification of AML incorporates and interrelated morphology, cytogenetics, molecular genetics and immunologic markers in an attempt to construct a classification that is clinically and prognostically valid. Under this classification the requisite blast percentage in the marrow is $\geq 20\%$. Hematopoietic stem cell transplantation is an established therapeutic modality in patients with AML. An alloreactive immunotherapeutic effect of donor cells has been demonstrated.

No other established therapy applied during complete remission offers as strong an anti-leukemic effect. Transplant-related morbidity and mortality, however, remain obstacles in the successful application of this treatment. More recently, reduced-intensity conditioning has been applied as a therapy for AML. Reduced-intensity conditioning, which includes potent immunosuppressive agents in addition to anti-leukemic agents, effectively permits engraftment of donor hematopoietic stem cells. Several studies have demonstrated that the morbidity and mortality are less with these regimens compared to myeloablative conditioning (4) (5). While the reduced intensity of the conditioning regimen has resulted in reduced non-relapse mortality in patients with AML, some studies have suggested a concomitant increase in relapse as a consequence of lowering the intensity of the cytotoxic agents(6). New conditioning regimens that increase the anti-leukemic effect while maintaining a low regimen toxicity profile, are therefore needed.

Chronic myeloid leukemia (CML) was the first neoplastic disease associated with a chromosomal aberration. The Philadelphia chromosome is a reciprocal t(9;22)(q34;q11) translocation that results in the production of the Bcr-Abl1 fusion protein (previously termed Bcr-Abl), a constitutively active tyrosine kinase. Elucidation of the molecular pathogenesis of CML led to the development of the tyrosine kinase inhibitor (TKI) STI-571, now known as imatinib mesylate. The Food and Drug Administration first approved imatinib in May 2001 for the treatment of patients with chronic-phase (CP) CML after failure of interferon alfa therapy and for the treatment of advanced CML. In December 2002, after positive results from the International Randomized Study of Interferon vs ST1571 (IRIS), imatinib was approved for the treatment of patients with newly diagnosed CP-CML. Use of imatinib as first-line therapy has resulted in complete cytogenetic responses (CCyRs) in 65% to 85% of patients with CML. Despite the successes of imatinib in treating CML, some patients' responses to treatment are inadequate. In the IRIS trial, approximately 30% of patients with newly diagnosed CP-CML who were randomized to receive imatinib did not achieve a CCyR within 1 year of treatment. In addition, approximately 10% of patients experienced relapse during 5 years of follow-up, including

approximately 10% who had achieved a CCyR. Higher rates of treatment failure occur in patients with accelerated- or blast-phase disease.

Allogeneic SCT is the only potentially curative treatment for CML. However, since the development of modern TKIs, allogeneic SCT is more commonly performed after patients have received imatinib and second-generation agents and is an important treatment option after treatment failure. Prior imatinib treatment does not adversely affect overall survival, progression-free survival, or nonrelapse mortality after allogeneic SCT, and second-generation TKIs do not appear to increase transplant-related toxic effects. Also, allogeneic SCT is probably the best available therapy for eligible patients with a T315I mutation.

1.2 Fludarabine and busulfan in conditioning regimens:

The combination of fludarabine and intravenous busulfan (FluBu) has become the most commonly used conditioning regimen for allogeneic transplantation. Its safety profile has compared favorably to the previous regimens of cyclophosphamide and TBI or cyclophosphamide and busulfan (BuCy). Andersson et al. reported on 148 patients receiving fludarabine and busulfan for conditioning regimen compared to 67 patients receiving BuCy (7). The groups had comparable pretreatment characteristics, except that FluBu patients were older (46 versus 39 years, $P<0.01$), more often had unrelated donors (47.3% versus 20.9%, $P<0.003$), and had shorter median follow-up (39.7 versus 74.6 months). To account for improved supportive care and other unidentified factors that might have affected outcome (“period” effects), 78 acute myelogenous leukemia (AML) patients receiving Melphalan-Flu (MF), treated in parallel during this time (1997-2004) were used to estimate the period effect. The MF patients’ outcomes worsened during this period. Therefore, the period effect was unlikely to have explained the greatly improved outcome with FluBu. Patients transplanted with FluBu in their first complete remission (CR1) had a 3-year overall survival and event-free survival (EFS) of 78% and 74% respectively, whereas CR1 patients younger than age 41 had a 3-year EFS of 83%. These results supported replacing BuCy with FluBu. Bredeson et al. compared BuCy to FluBu by performing a retrospective matched-pair analysis comparing outcomes of adult patients treated with either regimen (8). One hundred and twenty cases (FluBu) and 215 matched controls (BuCy) were available for comparison. All FluBu patients also received antithymocyte globulin (ATG). Patients receiving FluBu had significantly less treatment related mortality (12% versus 34%) and grades II-IV acute graft-versus-host disease (15% versus 34%, $P<0.001$) compared to BuCy patients. The risk of relapse however, was higher in the FluBu patients (42% versus 20%, $P<0.001$). The risk of chronic GVHD and disease-free survival was similar in the cases and controls. In conclusion, the FluBu regimen has improved the treatment-related mortality but post-transplant relapse remains the main obstacle in the successful treatment of these patients.

The fludarabine, busulfan, TBI (FluBuTBI) regimen has been established in an effort to reduce the relapse rate (9). Russell et al. evaluated a myeloablative regimen of daily busulfan, fludarabine, and 400 cGy total-body irradiation given before allogeneic transplantation. Sixty-four adults with acute leukemia in first and second remission were evaluated. All patients also received ATG. For 31 matched related and 33 alternate donor stem cell transplantation the overall treatment-related mortality was 3%. Projected disease-free and overall survival at 3 years for AML were the same at 83%, and for acute lymphoblastic leukemia were 65% and 78% respectively. For the matched related donors

the disease free survival was 77% and overall survival 87%, for alternative donors the disease free survival and overall survival were 71% and 84% respectively. Overall survival and disease free survival in patients without and with high-risk features were 100% versus 71% and 88% versus 68%, respectively. This combination therefore appears to be well tolerated and may offer better disease control than the standard FluBu.

2 STUDY RATIONALE

The combination of fludarabine and busulfan is the current standard of care for patients with myeloid malignancies (AML, CML and other myeloproliferative disorders, or MDS) undergoing allogeneic transplantation at HUMC. In this study we will be comparing in a randomized fashion the standard regimen to a regimen of fludarabine, busulfan and TBI.

2.1 Primary Objective

The primary objective is to compare the relapse rate at 1 year of patients with myeloid malignancies receiving each regimen.

2.2 Secondary Objectives

The secondary objective is to compare the toxicity of each regimen

3 INVESTIGATIONAL PLAN

3.1 Overall Design and Plan of Study

This is a single institution study of fludarabine and busulfan versus fludarabine, busulfan and low dose total body irradiation in patients undergoing allogeneic stem cell transplantation. A study population of 54 subjects will be enrolled from The John Theurer Cancer Center at Hackensack University Medical Center. Subjects who are eligible to receive allogeneic hematopoietic stem cell transplantation according to the eligibility criteria will be consented and enrolled. Subjects will be randomly assigned to receive one of 2 conditioning regimen: fludarabine and busulfan, or fludarabine busulfan and low dose total body irradiation (TBI). Subjects will be followed until 1 year post transplantation to assess the relapse rate in each arm and transplant-related toxicity

3.2 Patient Inclusion and Exclusion Criteria

3.2.1 Patient Inclusion Criteria

- 3.2.1.1 Diagnosis of acute myelogenous leukemia, chronic myelogenous leukemia, other myeloproliferative disorder, or myelodysplastic syndrome
- 3.2.1.2 Any stage of disease will be considered for transplantation
- 3.2.1.3 Have a suitable related or unrelated donor (Section 3.3)
- 3.2.1.4 Age ≥ 18 but <70 yrs
- 3.2.1.5 KPS of $\geq 70\%$
- 3.2.1.6 Recovery from all hematologic and non-hematology toxicities from previous therapies.

3.2.2 Patient Exclusion Criteria

Patients meeting any of the following exclusion criteria are not to be enrolled in the study.

- 3.2.2.1 Diagnosis other than acute myelogenous leukemia, myeloproliferative disorder, or myelodysplastic syndrome
- 3.2.2.2 Chemotherapy or radiotherapy within 14 days of initiating treatment in this study with the exception of lenalidomide, decitabine, azacitidine, imatinib mesylate, dasatinib, nilotinib hydrochloride and hydroxyurea.
- 3.2.2.3 Prior dose-intense therapy requiring HSC support within 56 days of initiating treatment in this study
- 3.2.2.4 Uncontrolled bacterial, viral, fungal or parasitic infections
- 3.2.2.5 Uncontrolled CNS metastases
- 3.2.2.6 Known amyloid deposition in heart
- 3.2.2.7 Organ dysfunction
 - 3.2.2.7.1 LVEF $<40\%$ or cardiac failure not responsive to therapy
 - 3.2.2.7.2 FVC, FEV₁, or DLCO $<50\%$ of predicted and/or receiving supplementary continuous oxygen
 - 3.2.2.7.3 Evidence of hepatic synthetic dysfunction, or total bilirubin $>2x$ or AST $>3x$ ULN

- 3.2.2.7.4 Calculated creatinine clearance <20 ml/min
- 3.2.2.8 Karnofsky score <70%
- 3.2.2.9 Life expectancy limited by another co-morbid illness
- 3.2.2.10 Diagnosed or treated for another malignancy within 3 years of enrollment, with the exception of complete resection of basal cell carcinoma or squamous cell carcinoma of the skin, an in situ malignancy, or low-risk prostate cancer after curative therapy
- 3.2.2.11 Female subject is pregnant or breast-feeding (women) or unwilling to use acceptable birth control methods (men or women) for twelve months after treatment. Confirmation that the subject is not pregnant must be established by a negative serum β -human chorionic gonadotropin (β -hCG) pregnancy test result obtained during screening. Pregnancy testing is not required for post-menopausal or surgically sterilized women.
- 3.2.2.12 Documented hypersensitivity to fludarabine or melphalan or to bortezomib, boron or mannitol or any components of the formulation
- 3.2.2.13 Patients unable or unwilling to provide consent
- 3.2.2.14 Myocardial infarction within 6 months prior to enrollment or has New York Heart Association (NYHA) Class III or IV heart failure (see section 8.4), uncontrolled angina, severe uncontrolled ventricular arrhythmias, or electrocardiographic evidence of acute ischemia or active conduction system abnormalities. Prior to study entry, any ECG abnormality at screening has to be documented by the investigator as not medically relevant
- 3.2.2.15 Patient has received other investigational drugs with 14 days before enrollment
- 3.2.2.16 Serious medical or psychiatric illness likely to interfere with participation in this clinical study

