3.4 Patient Evaluation

Pre-transplant evaluation must be performed within 30 days of transplantation.

- 3.4.1 History with full details of the patient's prior treatments and responses
- 3.4.2 Physical exam with determination of Karnofsky score and findings related to underlying malignancy
- 3.4.3 Chemistry profile to include serum creatinine, AST, alkaline phosphatase, and bilirubin
- 3.4.4 CBC with differential
- 3.4.5 ABO and Rh
- 3.4.6 Serum pregnancy test, if female gender with child-bearing potential
- 3.4.7 HIV, Hepatitis B, Hepatitis C, CMV serology
- 3.4.8 Disease Staging:
 - 3.4.8.1 Bone marrow aspiration and biopsy
 - 3.4.8.2 Morphology
 - 3.4.8.3 Cytogenetic evaluation
 - 3.4.8.4 Fish study for common abnormalities associated with the disease being treated (if previously documented negative, need not be repeated to comply with this requirement).
 - 3.4.8.5 Molecular testing for common abnormalities associated with the disease being treated
- 3.4.9 Pulmonary function tests with DLCO
- 3.4.10 MUGA scan or cardiac echo
- 3.4.11 EKG

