3.9 Study Medications

All medications used in this study are commercially available

3.9.1 Fludarabine:

Fludarabine is a fluorinated nucleotide analogue of the antiviral vidarabine. It acts as a purine antagonist antimetabolite. Synonyms: 2-F-ara-AMP. Bone-marrow suppression from fludarabine is dose-limiting, manifesting as neutropenia, thrombocytopenia, and anemia. Other adverse effects include fever, chills, cough, Dyspnea, pneumonia, gastrointestinal disturbances, stomatitis, edema, the tumor lysis syndrome, skin rashes, auto-immune hemolytic anemia and thrombocytopenia, and hemorrhagic cystitis. Neurological disturbances include peripheral neuropathy, agitation, confusion, visual disturbances, seizures, and coma; high doses have been associated with progressive encephalopathy, blindness, and death. Dosage should be reduced in renal impairment and fludarabine should not be given if creatinine clearance is less than 30 mL/minute. Intravenous fludarabine phosphate is rapidly dephosphorylated to fludarabine, which is taken up by lymphocytes and rephosphorylated to the active triphosphate nucleotide. Peak intracellular concentrations of fludarabine triphosphate are seen about 4 hours after a dose. Fludarabine has a bioavailability of about 50 to 65% after doses of the phosphate by mouth. Clearance of fludarabine from the plasma is triphasic with a terminal half-life of about 20 hours. Elimination is mostly via renal excretion: 60% of a dose is excreted in the urine. The pharmacokinetics of fludarabine exhibit considerable interindividual variation.

3.9.2 Busulfan:

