3.10 Outline of Treatment Plan

Eligible patients who have signed informed consent will undergo pre-transplant evaluation and clearance as per current transplant program standard operating procedures. Patients will be admitted to Hackensack University Medical Center for the administration of the fludarabine, busulfan, TBI and for the transplant procedures

Table 1: Treatment Schema for Conditioning Regimen

	Day of Transplant											
	-6	-5	-4	-3	-2	-1	0	+1	+3	+6	+9	+11
Fludarabine 40mg/m²	X	X	X	X								
Busulfan 130 mg.m²	X	X	X	X								
rATG				X	X	X						
TBI 200 cGY (as randomized)							X/ X					
Tacrolimus					X→							
Stem cell infusion							X					
Methotrexate 5 mg/m²							X	X	X		X	
Filgrastim 5 ug/kg										X→		

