3.10.1 Conditioning Regimens

Eligible patients who have signed informed consent will be randomized to treatment arm A (Flu-Bu) or treatment arm B (Flu-Bu-TBI).

3.10.2 Treatment arm A:

- 3.10.2.1 Patients must be admitted to HUMC prior to the start of the fludarabine and will not be discharged until engraftment has occurred.
- 3.10.2.2 Fludarabine will be administered at a dose of 40/mg/m² IV daily for 4 days starting on transplant day -6.
- 3.10.2.3 Busulfan will be administered immediately following the fludarabine at a dose of 130 mg/m² IV daily for 4 days starting on transplant day -6.
- 3.10.2.4 Patients will also receive rabbit antithymocyte globulin (Thymoglobulin) at a dose of 0.5 mg/kg IV on day -3, and 1.5 mg/kg on day -2 and 2 mg/kg on day -1
- 3.10.2.5 Hematopoietic cells will be infused on day 0
- 3.10.2.6 Graft versus host disease (GVHD) prophylaxis will consist of tacrolimus 0.03 mg/kg (or 0.015 mg/kg for age \geq 65) using ideal body weight, IV total daily dose starting on transplant day -2 and adjusted based on blood levels. Methotrexate at a dose of 5 mg/m² IV will be administered on transplant days +1, +3, +6 and +11
- 3.10.2.7 Dose adjustment for the fludarabine, busulfan and antithymocyte globulin will be as follows:
 - 3.10.2.7.1 If patient weighs less than 100% of ideal body weight (IBW), dosing is based on actual body weight
 - 3.10.2.7.2 If patient weighs 120-150% of IBW, dosing is based on adjusted body weight (ABW)
 - 3.10.2.7.3 If patient weighs greater than 150% of IBW, actual weight will be capped at 150% of ideal body weight, and this will be used in the adjusted body weight formula
- 3.10.2.8 Corrected body weight formula: ABW= IBW + [(0.25) x (actual BW-IBW)]

3.10.3 Treatment arm B:

- 3.10.3.1 Patients must be admitted to HUMC prior to the start of the fludarabine and will not be discharged until engraftment has occurred.
- 3.10.3.2 Fludarabine will be administered at a dose of 40/mg/m² IV daily for 4 days starting on transplant day -6.
- 3.10.3.3 Busulfan will be administered immediately following the fludarabine at a dose of 130 mg/m² IV daily for 4 days starting on transplant day -6.
- 3.10.3.4 Total body irradiation will be given in 2 fractions of 200 CGY (total 400 CGY) on day -1.

3.10.3.5 All patients in treatment arm B will also receive rabbit antithymocyte globulin (Thymoglobulin) at a dose of 0.5 mg/kg IV on day -3, and 1.5 mg/kg on day -2 and 2 mg/kg on day -1.

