3.10.3.6 Hematopoietic cells will be infused on day 0.

3.10.3.7 Graft versus host disease (GVHD) prophylaxis will consist of tacrolimus 0.03 mg/kg (or 0.015 mg/kg for age \geq 65) using ideal body weight, IV total daily dose starting on transplant day -2 and adjusted based on blood levels. Methotrexate at a dose of 5 mg/m² IV will be administered on transplant days +1, +3, +6 and +11.

3.10.3.8 Dose adjustment for the fludarabine, busulfan and antithymocyte globulin will be as follows:

- 3.10.3.8.1 If patient weighs less than 100% of ideal body weight (IBW), dosing is based on actual body weight.
- 3.10.3.8.2 If patient weighs 120-150% of IBW, dosing is based on adjusted body weight (ABW).
- 3.10.3.8.3 If patient weighs greater than 150% of IBW, actual weight will be capped at 150% of ideal body weight, and this will be used in the adjusted body weight formula.

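### Patients with creatinine clearance of 20 to below 30 mL/min may enrol and are prescribed full-dose fludarabine, which the protocol's own drug section says should not be given below 30 mL/min

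*Combined protocol and SAP*

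**What the plan says.** Three parts of the protocol bear on renal function and fludarabine.

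- **Eligibility.** Section 3.2.2 lists organ-dysfunction exclusions. The renal one (3.2.2.7.4) reads "Calculated creatinine clearance <20 ml/min". No other inclusion or exclusion criterion gives a renal limit.
- **Drug information.** Section 3.9.1 says of fludarabine: "Dosage should be reduced in renal impairment and fludarabine should not be given if creatinine clearance is less than 30 mL/minute". It adds: "Elimination is mostly via renal excretion: 60% of a dose is excreted in the urine".
- **Treatment.** For arm A (3.10.2.2), and in the same words for arm B (3.10.3.2): "Fludarabine will be administered at a dose of 40/mg/m² IV daily for 4 days starting on transplant day -6". Each arm then has a list introduced by "Dose adjustment for the fludarabine, busulfan and antithymocyte globulin will be as follows" (3.10.2.7 and 3.10.3.8). Every item in both lists concerns actual, ideal or adjusted body weight; none mentions renal function.

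Two further provisions matter. The screening work-up (3.4.3) includes "Chemistry profile to include serum creatinine, AST, alkaline phosphatase, and bilirubin". Under 3.10, consented patients "will undergo pre-transplant evaluation and clearance as per current transplant program standard operating procedures"; the content of those procedures is not given.

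**The concern.** The eligibility threshold and the drug warning are 10 mL/min apart, and the treatment sections do nothing to bridge the gap. Staff who work from the eligibility list and the treatment orders would enrol a patient at, say, 25 mL/min and give the full course. Staff who work from 3.9.1 would withhold the drug. Nothing in the protocol says which section governs.

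What is at stake is patient safety. The protocol itself describes fludarabine as mainly renally cleared, and in 3.9.1 it lists severe and even fatal neurological toxicity at high doses. The problem also reaches above 30 mL/min: 3.9.1 calls for a lower dose in renal impairment generally, but no section says what impairment triggers a reduction or how large it should be.

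**Working it through.** The plan gives no figure to reproduce on this point, so the check is mainly a comparison of the text.

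**Step 1: set the rules side by side.**

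| Calculated creatinine clearance | Eligible on renal grounds (3.2.2.7.4)? | Drug section (3.9.1) | Treatment sections (3.10.2, 3.10.3) |
|---|---|---|---|
| Below 20 mL/min | No | Do not give | Not applicable |
| 20 to below 30 mL/min | Yes | Do not give | 40 mg/m² × 4 days, weight adjustment only |
| 30 mL/min or above, renally impaired | Yes | Reduce (amount not stated) | 40 mg/m² × 4 days, weight adjustment only |
| 30 mL/min or above, not impaired | Yes | No renal restriction | 40 mg/m² × 4 days, weight adjustment only |

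In the second row the instructions cannot both be followed. In the third row a reduction is called for but no rule is supplied.

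**Step 2: dose prescribed in the conflict band.** 40 mg/m² per day × 4 days = 160 mg/m², in either arm, with no renal reduction.

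**Step 3: how many patients might be affected.** The documents do not give the share p of enrolled patients with a clearance of 20 to below 30 mL/min. The values below are assumptions that show a range; they are not evidence of frequency. With n = 54 (5.3 and 5.4) and patients treated as independent:

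- expected number = 54 × p
- chance of at least one = 1 − (1 − p)^54

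| Assumed p | Expected number among 54 | Chance of at least one |
|---|---|---|
| 0% | 0 | 0% |
| 1% | 0.54 | 42% |
| 2% | 1.08 | 66% |
| 5% | 2.70 | 94% |

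These are chances of enrolling such a patient. They are not chances that a full dose is actually given, or that harm follows.

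**Step 4: accrual effect of a stricter exclusion.** Planned accrual is 54 patients in four years, or 54 / 4 = 13.5 per year. Refilling 0 to 2.7 places takes 0 to 2.7 / 13.5 = 0.2 year, that is 0 to 2.4 months, under the same assumption.

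**The case against.** The strongest reply is that 3.9.1 belongs to the same protocol and already tells staff to reduce or withhold. Exclusion criteria decide who may enter and do not compel dosing, so a careful investigator who reads both sections would not give fludarabine below 30 mL/min. On that view only a cross-reference and a dose schedule are missing. This has some force: actual full-dose exposure in the band is not established. But 3.9.1 reads as a general drug description, and nothing ranks it above the treatment orders. A patient from whom fludarabine is withheld also does not receive either randomized regimen, and under 5.11 a departure from the regimen prompts action to improve compliance. The place to resolve this is screening.

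Other safeguards can be cited: recovery from earlier treatment toxicities (3.2.1.6), limited life expectancy from co-morbidity (3.2.2.9), serious medical illness (3.2.2.16), withdrawal on safety grounds (5.9.1.3 and 5.9.1.5), and program clearance under 3.10. Each might stop some of these patients. None states a renal limit, and the withdrawal clauses act only after enrolment. The program procedures may hold a renal rule, but that cannot be known from these documents.

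It is also fair to say that the affected group may be empty and that both arms carry the same text, so there is no obvious bias between them. Both points stand. They limit the consequence for the trial's results; they do not remove the contradiction.

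**Conclusion.** The concern holds. As written, a patient with a calculated creatinine clearance of 20 to below 30 mL/min is eligible on renal grounds and is prescribed 160 mg/m² of fludarabine over four days, although 3.9.1 says the drug should not be given. This conclusion rests on the text alone and needs no outside source or assumption.

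How often it would arise is unknown. The range of 0 to 2.7 patients among 54 depends entirely on an assumed share of 0% to 5%. The argument for correcting it does not rest on that range. It rests on two safety instructions that cannot both be followed, for a drug whose severe toxicity the protocol itself describes. The type I error, the power and the primary relapse comparison are not shown to be affected.

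A secondary gap is that renally impaired patients at 30 mL/min or above have no reduction schedule. A lesser wording fault lies in the allergy exclusion (3.2.2.12): it names melphalan and bortezomib, which neither arm gives, and does not name busulfan or rabbit antithymocyte globulin, which both arms give. That fault is separate and adds nothing to the weight of the renal point.

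**What to change.** 1. Change 3.2.2.7.4 to exclude calculated creatinine clearance below 30 mL/min. This is the default.
2. If the investigators do intend to treat at 20 to below 30 mL/min, amend 3.9.1 to say so, give the justification, and state the dose.
3. In either case, add a renal dose-reduction rule for fludarabine to 3.10.2.7 and 3.10.3.8, identical in both arms. The clearance bands and doses are for the investigators to set; the documents give no values.
4. As a tidy-up, revise 3.2.2.12 to remove melphalan and bortezomib and to name busulfan and rabbit antithymocyte globulin alongside fludarabine.

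The cost is a short amendment. No new test is required, since serum creatinine is already in the pre-transplant chemistry profile and the existing criterion already calls for a calculated clearance. A few candidates may no longer qualify; under the assumed 0% to 5% share, replacing them would take 0 to 2.4 months of accrual.

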Antithymocyte globulins are antibodies, which act against lymphocytes, and in particular against T-cells, to produce suppression of cell-mediated immunity. Common adverse reactions include fever, chills, and skin reactions including rash, pruritus, and urticaria, which may be manifestations of hypersensitivity. Dyspnea, hypotension, chest, back or flank pain may indicate anaphylaxis, which can occur in up to 1% of patients. Rashes and arthralgia may represent serum sickness, especially in patients with aplastic anemia. Use with other immunosuppressants may reduce the incidence or severity of hypersensitivity but increase the risk of acquired systemic infections, such as CMV or herpes simplex. Enhanced immunosuppression may also increase the incidence of post-transplant lymphoproliferative disease or other malignancies. Leucopenia and thrombocytopenia are also common. Although usually transient, dosage adjustment may be necessary if they become severe or prolonged, and if unrelenting, they may warrant stopping therapy. Other adverse effects include headache, abdominal pain, gastrointestinal disturbances, hypertension, peripheral edema, asthenia, hyperkalaemia, and tachycardia. Nephrotoxicity has been reported.

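### The hypersensitivity exclusion (3.2.2.12) names drugs this trial does not give and omits busulfan and rabbit antithymocyte globulin, which both arms receive

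*Combined protocol and SAP*

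**What the plan says.** Section 3.2.2 of the protocol is a binding list: a patient who meets any item may not be enrolled. Item 3.2.2.12 reads "Documented hypersensitivity to fludarabine or melphalan or to bortezomib, boron or mannitol or any components of the formulation".

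Section 3.9 (Study Medications) has three entries: fludarabine, busulfan and rabbit antithymocyte globulin. Section 3.10 gives all three to both arms:

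- **Busulfan.** Items 3.10.2.3 (arm A) and 3.10.3.3 (arm B) use the same sentence: "Busulfan will be administered immediately following the fludarabine", at 130 mg/m² daily for 4 days from day -6.
- **rATG.** Items 3.10.2.4 (arm A) and 3.10.3.5 (arm B) give 0.5, 1.5 and 2 mg/kg on days -3, -2 and -1.

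On rATG, section 3.9.3 warns of hypersensitivity and adds: "Dyspnea, hypotension, chest, back or flank pain may indicate anaphylaxis, which can occur in up to 1% of patients".

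**The concern.** An allergy exclusion should keep a patient with a known reaction to a study drug from being enrolled to receive it. This one does so for fludarabine only. It leaves out busulfan and rATG, although the protocol's own drug information singles out rATG for anaphylaxis. It also lists agents that nobody in the trial will receive.

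The stake is patient safety and a correct, auditable eligibility rule. For two of the three study medications, allergy screening rests on clinical judgment outside the written criteria. In the other direction, a screener who follows the protocol must turn away a patient for an allergy with no bearing on the treatment.

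**Working it through.** This is mainly a comparison of texts. The documents state no figure to reproduce.

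**Step 1. Compare the criterion with the treatment plan.**

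| Agent | Named in 3.2.2.12 | Given in the trial (3.9, 3.10, Table 1) |
|---|---|---|
| Fludarabine | yes | yes, both arms |
| Busulfan | no | yes, both arms |
| Rabbit antithymocyte globulin | no | yes, both arms |
| Melphalan | yes | no |
| Bortezomib | yes | no |
| Boron | yes | no |
| Mannitol | yes | not stated; possibly an excipient |

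The criterion covers 1 of the 3 medications in section 3.9. Three of its five named items are not in the treatment plan. If boron is counted together with bortezomib, beside which it stands, that is two drugs.

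**Step 2. Look for the stray agents elsewhere.** In the supplied text, melphalan otherwise appears only in section 1.2, in a historical cohort given melphalan and fludarabine and used to estimate a period effect. Bortezomib and boron appear nowhere else. Wording carried over from another protocol would explain this, but that is an inference.

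**Step 3. Does the closing phrase rescue the rule?** The reference to formulation components is in the singular and follows the list of named agents. It naturally means the formulation of what has just been listed. It does not bring in two drugs that the sentence never mentions.

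**Step 4. Does another criterion cover the gap?** No other item in 3.2.1 or 3.2.2 addresses drug allergy. The nearest are 3.2.1.6 (recovery from toxicities of previous therapy) and 3.2.2.16 (serious medical or psychiatric illness), and neither is an allergy rule. For donors, by contrast, item 3.3.2.4 does name the relevant agent, filgrastim.

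**Step 5. Could such a patient present?** Yes. Item 3.2.2.3 excludes earlier dose-intense therapy with stem cell support only if it fell within 56 days of study treatment. No criterion excludes prior busulfan or rATG.

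**Step 6. How many might there be?** The documents give no prevalence *p* of prior documented busulfan or rATG allergy, so *p* is assumed over a range. With n = 54 (sections 3.1 and 5.3), the expected number is n × p, and the chance of at least one is 1 − (1 − p)^n:

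| Assumed p | Expected number | Chance of at least one |
|---|---|---|
| 0.1% | 54 × 0.001 = 0.054 | 1 − 0.999^54 = 5.3% |
| 0.5% | 54 × 0.005 = 0.27 | 1 − 0.995^54 = 23.7% |
| 1% | 54 × 0.01 = 0.54 | 1 − 0.99^54 = 41.9% |

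The 1% in section 3.9.3 is a ceiling on reactions during treatment, a different quantity, and is not the source of *p*.

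**The case against.** The strongest reply is that no one is likely to be harmed. The pre-transplant work-up takes a history with full details of "prior treatments and responses" (3.4.1). Patients undergo "pre-transplant evaluation and clearance as per current transplant program standard operating procedures" (3.10). Item 5.9.1.3 requires withdrawal on safety grounds. Busulfan and rATG are given at identical doses on identical days in both arms, so the omission cannot favour either one. On this view the point is a minor drafting slip.

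Much of this stands. The safeguards are real, and the comparison between arms is untouched. But none of them is a stated allergy rule, and withdrawal acts only after enrollment. Nor do they help the patient whom the rule needlessly bars, since a screener has to apply the list.

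Two further objections have partial force. First, the assumed prevalences have no basis in the documents. The table shows the chance that an allergic patient is present, not the chance of harm, and the upper figure follows from the chosen ceiling. The firm evidence is the mismatch in the text. Second, both arms also receive tacrolimus, methotrexate and filgrastim, and the criterion names none of these either. Where the list should end is partly a matter of preference. The three medications that the protocol itself describes in section 3.9 are a reasonable minimum.

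**Conclusion.** The concern holds. Item 3.2.2.12 is wrong as written, in both directions: it fails to exclude documented allergy to two of the three study medications, and it excludes allergy to agents the trial does not use. This conclusion rests on the text alone, and on reading the closing phrase as tied to the agents named before it.

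The practical effect is probably small. The number of affected patients is unknown and may be zero, and other clinical checks would probably catch an allergic patient. Sample size, power, significance level and the primary analysis are unaffected. It should still be corrected, because it is a mandatory safety criterion and the correction costs very little.

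**What to change.** Replace 3.2.2.12 with: *Known allergy, on record, to fludarabine, busulfan, rabbit antithymocyte globulin (or rabbit proteins), or any component of their formulations.* Delete melphalan, bortezomib and boron. Keep mannitol only if the pharmacy confirms that a product given in this trial contains it; the words on formulation components would then cover it anyway. The mention of rabbit proteins is a suggestion for the investigator and pharmacy to confirm, since the protocol does not discuss it. Adding tacrolimus, methotrexate and filgrastim is optional.

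The cost is a one-line eligibility amendment with IRB approval (section 6.2) and an updated screening checklist. The downside is at most a rare additional screen failure, partly offset by no longer refusing patients for allergy to drugs that are not given.
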